The procedure above ensures participants are incentivized to answer the questions as though they were really shopping for beverages in an online store. Sending participants the products is common economics experiments designed to simulate online shopping, and has been used in a variety of studies by members of this research team. [name] and [name] (2015) asks participants whether they would prefer environmentally friendly lightbulbs to standard lightbulbs at different prices, and send lightbulbs to participants based on their responses. Both [name] and Rees-Jones (2018) and [name] and [name] (2020) have participants answer questions about whether or not participants would be willing to buy common household products at certain prices, and based on their responses, ship some participants products.

• Within 2-3 weeks from the end of the survey, we will ship the selected beverages to the participants using the shipping information they provide us.

PROTOCOL
Soc-Behav-Ed Exempt
Berkeley

Protocol # 2020-08-13558
Date Printed: 08/17/2021

Protocol Title: Optimal non-financial policy instruments: fuel-efficient cars and sugar-sweetened beverages

Protocol Type: Soc-Behav-Ed Exempt

Date Submitted: 06/27/2021

Important Note: This Print View may not reflect all comments and contingencies for approval. Please check the comments section of the online protocol. Questions that appear to not have been answered may not have been required for this submission. Please see the system application for more details.

• We include the 2-3 day waiting period between Parts I and II to minimize bias in the Part II responses. Without the waiting period, participants might be more inclined to focus on the nutritional aspects of the beverage than they would in their regular purchasing decisions.

b) State if photographing, audio, or video recording will occur and for what purpose (e.g. transcription, coding facial expressions).

N/A

c) Alternatives to Participation

Describe appropriate alternative resources, procedures, courses of treatment, if any, that are available to prospective subjects. If there are no appropriate alternatives to study participation, this should be stated. If the study does not involve treatment/intervention, enter "N/A" here.

N/A

d) If the proposed research involves secondary use of data/specimens, check all that apply:

i) coded private information or specimens, and the investigator will not have access to the key.

ii) from publicly available sources.

iii) recorded by the investigator in such a manner that subjects cannot be identified OR any link to identifying information has been destroyed.

PROTOCOL
Soc-Behav-Ed Exempt
Berkeley

Protocol # 2020-08-13558
Date Printed: 08/17/2021

Protocol Title: Optimal non-financial policy instruments: fuel-efficient cars and sugar-sweetened beverages

Protocol Type: Soc-Behav-Ed Exempt

Date Submitted: 06/27/2021

Important Note: This Print View may not reflect all comments and contingencies for approval. Please check the comments section of the online protocol. Questions that appear to not have been answered may not have been required for this submission. Please see the system application for more details.

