- Participants will first be given a brief description of the study and asked to provide their consent online via a yes/no question (they must select "yes" to continue). The consent form conforms to Berkeley guidelines. In particular, the consent form will include (i) the identity and affiliation of our research team, (ii) a clear description of the study procedures (including that they will be randomly assigned to one of several possible treatment arms) and how data will be used, (iii) a statement that this is a research study and that participation is voluntary, (iv) contact information from a member of our research team and for UC Berkeley CPHS for questions about the research, (v) the CPHS protocol ID number, and (vi) a notice that the research team will obtain their AmeriSpeak demographic survey responses from AmeriSpeak and link those demographic survey responses to their fuel cost survey responses.
- Participants will then answer some introductory questions, including listing their county and state of residence in 2019, estimating how many miles they drove with their primary vehicle in 2019, and estimating of gas costs per gallon in 2019.
- Participants will then be asked to rate four cars on a scale of 1-10 for how much they would like having the car. They are then asked to say how much they would be willing to pay for the car, if the gas were free.
- Participants are then given instructions for the rest of the survey, including how they can earn a bonus

PROTOCOL
Soc-Behav-Ed Exempt
Berkeley

Protocol # 2020-08-13558
Date Printed: 08/17/2021

Protocol Title: Optimal non-financial policy instruments: fuel-efficient cars and sugar-sweetened beverages
Protocol Type: Soc-Behav-Ed Exempt
Date Submitted: 06/27/2021
Important Note: This Print View may not reflect all comments and contingencies for approval. Please check the comments section of the online protocol. Questions that appear to not have been answered may not have been required for this submission. Please see the system application for more details.

payment. Specifically, participants will be shown two cars and asked a series of questions about whether they would prefer to buy car A for \$X or car B for \$2,000. For each purchase, we compute a net annual value as:

o the maximum they told us earlier that they would pay per year to lease the car if gas is free,

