- Participants will first be given a brief description of the study and asked to provide their consent online via a yes/no question (they must select "yes" to continue). The consent form conforms to Berkeley guidelines. Participants will first be given a brief description of the study and asked to provide their consent online. The consent form conforms to Berkeley guidelines. In particular, the consent form will include (i) the identity and affiliation of our research team, (ii) a clear description of the study procedures (including that they will be randomly assigned to one of several possible treatment arms) and how data will be used, (iii) a statement that this is a research study and that participation is voluntary, (iv) contact information from a member of our research team and for UC Berkeley CPHS for questions about the research, and (v) the CPHS protocol ID number. They will also be told that we will ask for their email address, name, and shipping address in order to send them their rewards.
- Participants will also be asked to enter their email address, which is how we will inform them to complete Part II of the survey.
- Participants will then answer questions on basic demographic information (such as age, education, and income), their preferences for sugar-sweetened beverages, and a series of nutritional knowledge questions. This concludes Part I of the survey.
- At the end of Part I, participants will be told Part II that we will send a follow-up survey in 2-3 days via

PROTOCOL
Soc-Behav-Ed Exempt
Berkeley

Protocol # 2020-08-13558
Date Printed: 08/17/2021

Protocol Title: Optimal non-financial policy instruments: fuel-efficient cars and sugar-sweetened beverages

Protocol Type: Soc-Behav-Ed Exempt

Date Submitted: 06/27/2021

Important Note: This Print View may not reflect all comments and contingencies for approval. Please check the comments section of the online protocol. Questions that appear to not have been answered may not have been required for this submission. Please see the system application for more details.

email.

- After 2-3 days, participants will receive the follow-up survey. Only those who completed Part I will be eligible to complete this survey.
- Participants will first be asked to give their consent again.
- Participants will then select their favorite sugar-sweetened beverages from a list.

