- Participants will be told they are shopping for sugar-sweetened beverages and asked to enter their name and the address where they want the product shipped.
- Participants will then be shown a picture of one of these sugar-sweetened beverages and a similar sugar free beverage (e.g., Minute Maid Lemonade and LaCroix Lemon). They will then answer a series of questions about whether they would prefer to buy the sugar-sweetened beverage for \$X or the sugar-free beverage for \$Y. Participants will answer these questions for three pairs of beverages, and are told they have a 1/3 chance of actually receiving beverages per one of their decisions.
- Participants will then be shown three more pairs of beverages with additional information displayed on the screen (the "treatment"). All information provided will be true and factual. They will randomly be shown one of the following: (i) nothing (the control group), (ii) the nutrition labels for each beverage, (iii) a graphic warning label, or (iv) a warning label with text outlining negative health consequences of drinking beverages with added sugar.
- Total participation time is approximately 10-20 minutes to complete both parts of the survey. All questions for both parts of the survey are attached (attachment_survey(ssb_part1 and attachment_survey(ssb_part2).

• Participants will be paid \$6 for completing this survey: \$2 for completing part I and \$4 for completing part II.

• Additionally, all participants will receive an additional \$7.00 budget. For these participants, we will randomly choose one of the purchase decisions, and they will receive their choice of beverage (either the sugar-sweetened beverage or the sugar-free beverage) and \$7.00 minus the price of the drink. For example, if on the randomly chosen question, participants say they prefer Minute Maid Lemonade for \$4.50 to LaCroix Lemon for \$3.00, then they will receive the Minute Maid Lemonade and an additional \$2.50.

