2. When the government can additionally set an optimal tax or subsidy, the incremental welfare from the information label is:

$$\left(\frac{1}{2} \text{Var}[\tau] + \text{Cov}[\tau, \gamma] \right) D_p(p)$$

The proposition states that the welfare effects of the information label depend on two terms: the heterogeneity of treatment effects, $\text{Var}[\tau]$, and the extent to which the treatment effects are well-targeted, $\text{Cov}[\tau, \gamma]$. Welfare is decreasing in $\text{Var}[\tau]$ holding constant $\text{Cov}[\tau, \gamma]$, as this large un-targeted heterogeneity generates misallocation in which individuals purchase which products. the extent to which it reduces the variances of bias: $\text{Var}[\tau + \gamma] - \text{Var}[\gamma]$. To obtain some intuition for this result, note that $\frac{1}{2} \text{Var}[\tau] + \text{Cov}[\tau, \gamma] = \text{Var}[\tau + \gamma] - \text{Var}[\gamma]$. Since $\tau + \gamma$ represents the “post-label” bias, the welfare effects of the label are thus proportional to how much the label reduces (or increases) the variance of bias in the population.

In the absence of a financial instrument, the welfare effects of the label also depend on $E[\tau]^2 + 2E[\tau]E[\gamma]$. Note that these terms are functions of $E[\tau]$, the average treatment effect. Intuitively, even if the label does not reduce the variance of bias, and instead simply functions as a blunt policy instrument that affects everyone in the same way, it is still useful because it functions as a substitute for a tax. The term $\rho \mu E[\tau|p] D_p$ simply corresponds to the extent to which labels counteract (or amplify) market power. E.g., if firms price too high, then a modest bias that leads consumers to overestimate the marginal value of the product may be optimal.

Econometric details. Recall that in the experiment, all subjects first make a decision in the absence of any labels (decision set $j = 1$), and then again with the potential presence of a label (decision set $j = 2$). We decompose willingness to pay of person i in decision set $j \in \{1,2\}$ for product k in label treatment T as follows:

$$w_{ijk}(T) = v_{ijk} + \gamma_{ik} + \tau_{ik}(T) \cdot I(j = 2)$$

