where $\tau_{ik}(T)$ is the treatment effect on person i for product k , γ_{ik} is the bias, and v_{ijk} is the true cost or benefit of getting the sugary rather than the sugarless drink. Our multiple price lists provide direct estimates of $w_{ijk}(T)$. We obtain estimates of bias, $\widehat{\gamma}_{ik}$, using the methodology of [name], Lockwood, and [name] (2019a) and the stage 1 survey questions. Before we detail the methodology of obtaining these estimates, we summarize the approach we take with those estimates in hand.

We make the following identifying assumptions, which essentially state that the measurement error in $\widehat{\gamma}$ is independent of the treatment effects.

$$E[v_{ijk}|T] \text{ does not depend on } T \text{ or on } j$$

$$\text{Cov}[v_{i2k} - v_{i1k}, \tau_{ik}] = 0$$

$$\text{Cov}[\gamma_{ijk} - \widehat{\gamma}_{ijk}, \tau_{ik}] = 0$$

$$\text{Cov}[\gamma_{ip} - \widehat{\gamma}_{ik}, v_{ijk} - v_{ij'k}] = 0$$

Under these assumptions, we obtain the following equation for the average (across the six products) variance of a given label:

$$\frac{1}{6} \sum_j Var[\tau_j | T = t] = \frac{1}{6} \sum_j (Var[\Delta w_{ij} | T = t] - Var[\Delta w_{ij} | T = 0])$$

Where $\Delta w_{ij} := w_{ij2} - w_{ij1}$ is the difference in WTP for the same product-pair $\$j\$$ before seeing the label versus after seeing the label.

We also obtain the following formula for the average covariance of the label with the bias:

$$\frac{1}{6} \sum_j Cov[\tau_j, \gamma_j | T = t] = \frac{1}{6} \sum_j (Cov[\Delta w_{ij}, \hat{\gamma}_i | T = t])$$

From this, it we can also immediately obtain the following statistics:

$$Var[\tau + \gamma] - Var[\gamma] = Var[\tau] + 2Cov[\tau, \gamma]$$

$$E[(\tau + \gamma)^2] - E[\gamma^2] = Var[\tau] + 2Cov[\tau, \gamma] + E[\tau]^2 + 2E[\tau]E[\gamma]$$

Estimating bias. We estimate each participant's bias using methods from [name], Lockwood, and [name] (2019a). Specifically, we assume bias is driven by a lack of nutritional knowledge and/or a lack of self-control.

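### Do the further beverage pairs in the protocol undermine the SAP's before-and-after difference for the same pair?

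*Protocol*

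**What the plan says.** Protocol section 4(a), part II (sugar-sweetened beverages survey), describes the Part II tasks in order. "Participants will then select their favorite sugar-sweetened beverages from a list". For the unlabelled stage, "Participants will answer these questions for three pairs of beverages". For the randomised stage, "Participants will then be shown three more pairs of beverages with additional information displayed on the screen". The section introduces these accounts as brief descriptions and says that copies of the surveys are attached. Section 8 lists the Part II instrument.

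The SAP, under Econometric details, has every subject decide first without labels, "and then again with the potential presence of a label". Its model is w_ijk(T) = v_ijk + γ_ik + τ_ik(T)·I(j = 2), introduced with the words "We decompose willingness to pay of person i in decision set", so j is the decision set and k the product. Δw is the "difference in WTP for the same product-pair" before and after the label. It feeds two formulas, each averaged with a factor 1/6:

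- Var[τ] is estimated by Var[Δw | T = t] − Var[Δw | T = 0]. The SAP calls this the "average (across the six products) variance of a given label".
- Cov[τ, γ] is estimated by Cov[Δw, γ̂ | T = t], with no control-arm term.

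**The concern.** The protocol's wording suggests three pairs before randomisation and three different pairs after it, and three plus three gives the SAP's six. No protocol sentence in the available text says that pairs repeat. On that reading no pair has both a before and an after value, and Δw as defined cannot be computed.

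The stake would be large. At the optimal tax the SAP gives the label's welfare effect as (½Var[τ] + Cov[τ, γ])·D_p. Its Related Preliminary Work reports a covariance near zero, so the pilot's finding that labels lower welfare under that tax rests mainly on Var[τ]. Same-pair baselines that were never collected could not be recovered later.

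The SAP's notation seems to add to the doubt. Its formula is Δw_ij = w_ij2 − w_ij1, where j is now the product pair. Read in the index order of the model, it would subtract one product from another within a single decision set.

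**Working it through.** **1. The plan's own figure.** The issue is one of wording, but the planned precision can be reproduced. The SAP gives a pilot interval width of $0.50 with 90 per arm, and plans 500 per arm. √(1000/180) = 2.357, and 0.50/2.357 = $0.212, which agrees with the stated $0.21. Treating the interval as a comparison of mean Δw, the implied SD is 0.25/1.96/√(2/90) = $0.856.

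**2. Does the SAP fix the pair?** Three features say so:

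- The definition of Δw names the same pair, before and after.
- In the model, γ_ik has no decision-set index, and product k is common to j = 1 and j = 2.
- The assumption Cov[v_i2k − v_i1k, τ_ik] = 0 compares one product across the two sets. It would have no role if the products changed.

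Against these, Δw_ij = w_ij2 − w_ij1 is a change of index order and not a different estimand.

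**3. Same pair.** In the label arm Δw = (v_i2k − v_i1k) + τ_ik, and in the control arm Δw = v_i2k − v_i1k. γ_ik cancels. The difference in variances is Var[τ] + 2Cov[τ, v_i2k − v_i1k] = Var[τ] under the stated assumption. γ also drops out of the Δw used in the covariance formula.

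**4. Different pairs, as a hypothetical.** Let u = v + γ. The difference in variances becomes Var[τ] + 2Cov[τ, u_after − u_before] = Var[τ](1 + 2rk). Here r = corr(τ, u_after − u_before) and k (now a ratio, not the product index) = SD(u_after − u_before)/SD(τ). At r = 0 there is no error. The estimate reaches zero at r = −1/(2k), which is −0.50, −0.25 and −0.17 for k = 1, 2 and 3. The documents give neither r nor k.

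The range can be illustrated with inputs that are all assumed: residual SD of τ $0.50, τ falling by 0.3 per $1 of product-specific bias, and half of the product-specific variance of u due to bias. At a product-specific SD of $1.0 the bias variance is 0.5. True Var[τ] is 0.25 + 0.09 × 0.5 = 0.295, and the cross-pair value is 0.295 − 2 × 0.3 × 0.5 = −0.005.

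| Product-specific SD | True Var[τ] | Same pair (simulated) | Different pairs (simulated) |
|---|---|---|---|
| $0.5 | 0.262 | 0.261 | 0.188 |
| $1.0 | 0.295 | 0.296 | −0.005 |
| $1.5 | 0.352 | 0.352 | −0.323 |

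The covariance formula, having no control-arm term, would also pick up Cov[u_after − u_before, γ̂]. An assumed extra SD of $1.0 from switching products would widen the treatment-effect interval to 2 × 1.96 × √(0.856² + 1.0²) × √(2/500) = $0.33.

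**5. Is that hypothetical the plan?** Neither document proposes differencing across pairs. The car survey uses parallel wording for its second stage, although "Participants will then be asked to rate four cars on a scale of 1-10" is its only valuation step. Two sets of two cars followed by two sets of new cars would need eight cars. In that template, *more* therefore cannot mean wholly new products. This supports repetition without proving it, since four cars form six distinct pairs.

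**6. Three pairs and six products.** Six may be a pool from which each participant prices three favourites, which fits the selection step. It may be six beverages in three repeated pairs. It may be three plus three distinct pairs, which the SAP's definition of Δw excludes. Under either surviving reading, the analyst averages over the pairs actually priced.

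**The case for a change.** The best case for acting has four parts:

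- The SAP is dated April 1, 2021. The amended protocol was submitted on 06/27/2021 and approved on 08/17/2021, so the SAP cannot be taken as the later, corrected account.
- The car section says that participants answer again in the second stage. The beverage section does not say even that.
- The pilot's positive variance does not prove repetition, because a cross-pair difference can also be positive.
- A clarification would cost one protocol sentence and two SAP lines, whereas missing baselines could not be repaired.

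The textual points stand: the protocol summary does not state repetition, the link from three pairs to six products is unwritten, and j is used for two things. The inference to a faulty design does not stand. The order of dates matters little when the SAP defines the estimand explicitly and the protocol sentence admits both readings. Harm requires the survey to have been programmed from that sentence, yet the protocol refers to instruments already written and attached. Nor is Var[τ] uniquely exposed. The covariance as the SAP writes it also relies on γ cancelling, so the whole SAP analysis presupposes repeated pairs.

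**Conclusion.** No change is needed. This is a loosely worded summary beside an explicit analysis definition, together with a clerical slip in an index. Following the SAP as written gives a well-defined Δw, and extra wording would only record what is already intended, with no effect on the data or the estimates.

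If the pairs repeat, the error is zero and the planned width of about $0.21 is unaffected. If they did not, the Var[τ] and Cov[τ, γ] formulas would both need added assumptions. The mean effect would still be estimable from the second-stage contrast between label and control. The size of any error is then unknown, because every figure in the illustration depends on assumed inputs.

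The conclusion rests on the Part II instrument repricing the same pairs. The SAP requires this and nothing in the documents shows otherwise, but the instrument was not available to confirm it.

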*** Subject Population ***

5. Subject Population

Describe proposed subject population, including criteria for study inclusion and exclusion (e.g., age, health status, language, gender, race, ethnicity). State the maximum number of subjects planned for the study. This number should account for all subjects to be recruited, including those who may drop out or be found ineligible.

For the sugar-sweetened beverages survey, our study population consists of participants recruited via Facebook ads who are shopping for soda. We aim to recruit a sample that will be broadly representative of the U.S. population in terms of race, gender, and education. We plan to overrecruit adults aged 65 or older so that they comprise approximately 25% of our sample. All U.S. residents aged 18 years or older will be eligible to enroll in our experiment.

For the fuel cost survey, our study population consists of AmeriSpeak panelists who own or are leasing a car. The survey will be advertised to AmeriSpeak panelists using a generic title (to avoid biasing respondents), as is common on these surveys: "Answer a 10-20 minute decision choice survey. You must own or be leasing a car to take this survey." All panelists are at least 18 years old. In addition, AmeriSpeak will work to ensure our subject population is nationally-representative along key demographics (race, gender, age, income, and education).

The maximum number of subjects planned for the study is 2,000 workers for the fuel cost survey and 3,000 workers for the sugar-sweetened beverages survey.

PROTOCOL
Soc-Behav-Ed Exempt
Berkeley

Protocol # 2020-08-13558
Date Printed: 08/17/2021

Protocol Title: Optimal non-financial policy instruments: fuel-efficient cars and sugar-sweetened beverages

Protocol Type: Soc-Behav-Ed Exempt

Date Submitted: 06/27/2021

Important Note: This Print View may not reflect all comments and contingencies for approval. Please check the comments section of the online protocol. Questions that appear to not have been answered may not have been required for this submission. Please see the system application for more details.

